Patients with suspected HLH should be diagnosed according to published criteria by McClain and Eckstein (2014). A patient should be classified as having HLH if five of the following eight criteria are met:

- *Fever $\geq 38.5^{\circ}\text{C}$*
- *Splenomegaly*
- *Peripheral blood cytopenia consisting of at least two of the following:*
 - *Hemoglobin < 90 g/L (9 g/dL) (< 100 g/L [10 g/dL] for infants < 4 weeks old)*
 - *Platelet count $< 100 \times 10^9/\text{L}$ (100,000/ μL)*
 - *ANC $< 1.0 \times 10^9/\text{L}$ (1000/ μL)*
- *Fasting triglycerides > 2.992 mmol/L (265 mg/dL) and/or fibrinogen < 1.5 g/L (150 mg/dL)*
- *Hemophagocytosis in bone marrow, spleen, lymph node, or liver*
- *Low or absent natural killer cell activity*
- *Ferritin > 500 mg/L (500 ng/mL)*
- *Soluble interleukin 2 (IL-2) receptor (soluble CD25) elevated ≥ 2 standard deviations above age-adjusted laboratory-specific norms*

Patients with suspected MAS should be diagnosed according to published criteria for systemic juvenile idiopathic arthritis by Ravelli et al. (2016). A febrile patient should be classified as having MAS if the following criteria are met:

- *Ferritin > 684 mg/L (684 ng/mL)*
- *At least two of the following:*
 - *Platelet count $\leq 181 \times 10^9/\text{L}$ (181,000/ μL)*
 - *AST ≥ 48 U/L*
 - *Triglycerides > 1.761 mmol/L (156 mg/dL)*
 - *Fibrinogen ≤ 3.6 g/L (360 mg/dL)*

Patients with suspected HLH or MAS should be treated according to the guidelines in [Table 14](#).

Appendix 11

Risks Associated with Atezolizumab and Guidelines for Management of Adverse Events Associated with Atezolizumab (cont.)

Table 14 Management Guidelines for Suspected Hemophagocytic Lymphohistiocytosis or Macrophage Activation Syndrome

Event	Management
Suspected HLH or MAS	
 • Permanently discontinue atezolizumab and contact Medical Monitor. • Consider patient referral to hematologist. • Initiate supportive care, including intensive care monitoring if indicated per institutional guidelines. • Consider initiation of IV corticosteroids, an immunosuppressive agent, and/or anti-cytokine therapy. • If event does not respond to treatment within 24 hours, contact Medical Monitor and initiate treatment as appropriate according to published guidelines (La Rosée 2015; Schram and Berliner 2015; La Rosée et al. 2019). • If event resolves to Grade 1 or better, taper corticosteroids over ≥ 1 month.

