4.6.2 Study Treatment Discontinuation

Patients must permanently discontinue study treatment if they experience any of the following:

- Confirmed disease progression or loss of clinical benefit (see Section 3.1.2 for dosing beyond progression)
- Symptomatic deterioration attributed to disease progression, as determined by the investigator, after integrated assessment of radiographic data, biopsy results, and clinical status
- Intolerable toxicity related to any study drug
- Any medical condition that the investigator or Sponsor determines may jeopardize the patient's safety if he or she continues to receive study treatment
- Use of another non-protocol-specified anti-cancer therapy (see Section 4.4.2)
- Pregnancy
- Withdrawal of consent
- Investigator or Sponsor determines it is in the best interest of the patient (e.g., unwillingness to comply with study assessments that compromise their safety)
- Any adverse event that requires study treatment discontinuation per the guidelines in Section 5.1, Appendix 10, and Appendix 11.

- In cases where discontinuation of one study drug is required for toxicity, patients may continue on the remaining drug (Arm A only) per the guidelines in Section 5.1 and Appendix 10.

The primary reason for study drug discontinuation should be documented on the appropriate eCRF. Patients who discontinue study treatment will not be replaced.

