5.1.5.3 Management of Cobimetinib- and Atezolizumab-Specific Adverse Events (Arm A)

Toxicities associated or possibly associated with cobimetinib plus atezolizumab treatment should be managed according to standard medical practice.

For management of cobimetinib- and atezolizumab-specific toxicities, including IRRs, gastrointestinal toxicity, dermatologic toxicity, hepatotoxicity, pulmonary toxicity, potential eye toxicity, reductions in LVEF from baseline, rhabdomyolysis, elevated CPK, and hemorrhage, see [Appendix 10](#).

Guidelines for management of patients who experience atezolizumab-associated or possibly associated adverse events, including infusion-related reactions and immune-mediated reactions (e.g., pulmonary, hepatic, gastrointestinal, endocrine, ocular, myocarditis, pancreatic, dermatologic, neurologic, meningoencephalitis, and renal events) are provided in [Appendix 11](#).

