Appendix 10 Management of Cobimetinib plus Atezolizumab-Associated Adverse Events (Arm A)

Note: For information regarding management of atezolizumab-associated adverse events, please refer to [Appendix 11](#).

Guidelines for Management of Cobimetinib plus Atezolizumab Adverse Events

Event	Action to Be Taken
General guidance for dose modifications and treatment delays and discontinuation	
 • There will be no dose modifications for atezolizumab. • If atezolizumab is withheld and corticosteroids are initiated for an atezolizumab-related toxicity, corticosteroids must be tapered over ≥ 1 month to ≤ 10 mg/day oral prednisone or equivalent before atezolizumab can be resumed.^{a, b, c} 
The dose of cobimetinib can be reduced by 20 mg (one dose level) up to two times (i.e., from 60 mg to 40 mg and then from 40 mg to 20 mg). If further dose reduction is indicated after two dose reductions, the patient must discontinue cobimetinib but may continue treatment with atezolizumab at the investigator's discretion.
 
 • If cobimetinib is withheld for > 28 days because of toxicity, the patient should be discontinued from cobimetinib, unless resumption of treatment is approved by the Medical Monitor after discussion with the investigator. • After dose reduction, consideration may be given to allow for dose escalation of cobimetinib by a maximum of one dose level following resolution of the adverse event that resulted in dose modification, provided there are no safety concerns. • If atezolizumab is withheld for > 12 weeks because of toxicity, the patient should be discontinued from atezolizumab, unless resumption of treatment is approved by the Medical Monitor after discussion with the investigator.
IRRs, CRS, anaphylaxis, and hypersensitivity reaction	
 • Guidelines for management of IRRs and CRS are provided in the Atezolizumab Investigator's Brochure and Appendix 11 • For anaphylaxis precautions, see Appendix 7. • For severe hypersensitivity reactions, permanently discontinue all study treatment.

CRS = *cytokine-release syndrome*; IRR = infusion-related reaction.

^a If corticosteroids have been initiated, they must be tapered over ≥ 1 month to ≤ 10 mg/day oral prednisone or equivalent before atezolizumab can be resumed.

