^b Atezolizumab may be withheld for a period of time beyond 105 days to allow for corticosteroids to be reduced to ≤ 10 mg/day oral prednisone or equivalent. The acceptable length of the extended period of time must be agreed upon by the investigator and the Medical Monitor.

^c Resumption of atezolizumab may be considered in patients who are deriving benefit and have fully recovered from the immune-mediated event. Patients can be rechallenged with atezolizumab only after approval has been documented by both the investigator (or an appropriate delegate) and the Medical Monitor.

Appendix 10

Management of Cobimetinib plus Atezolizumab-Associated Adverse Events (Arm A) (cont.)

GASTROINTESTINAL TOXICITY

Diarrhea and colitis have been associated with the administration of cobimetinib plus atezolizumab (see Section [5.1.1.3.2](#)).

See [Table 1](#) for guidelines on how to manage gastrointestinal toxicity in patients treated with cobimetinib plus atezolizumab.

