Appendix 10 Management of Cobimetinib plus Atezolizumab-Associated Adverse Events (Arm A) (cont.)

GUIDELINES FOR MANAGEMENT OF PATIENTS WHO EXPERIENCE HEMORRHAGE

Hemorrhage has been reported with cobimetinib (see Section 5.1.1.1.1) and should be managed according to the guidelines in Table 8.

Table 8 Recommended Dose Modifications in Patients with Hemorrhage

Event	Action to Be Taken
Hemorrhage	
Grade 3 hemorrhage	
 • Interrupt cobimetinib treatment. There are no data on the effectiveness of cobimetinib dose modification for hemorrhage events. Clinical judgment should be applied when considering restarting cobimetinib treatment. • Continue atezolizumab treatment.
Grade 4 hemorrhage or any grade cerebral hemorrhage	
 • Interrupt cobimetinib treatment. Permanently discontinue cobimetinib for hemorrhage events attributed to cobimetinib. • Continue atezolizumab treatment.
Grade 3 or 4 or intolerable Grade 2 treatment-related toxicities not described above and Table 3 (dose modifications for cobimetinib)	
 • Withhold all study treatment. • If event resolves to Grade 1 or better within 12 weeks, resume atezolizumab at fixed dose. If not, permanently discontinue atezolizumab.^{a, b, c} • If event resolves to Grade 1 or better within 28 days, resume cobimetinib with dose reduced by one level. If not, permanently discontinue cobimetinib.

^a If corticosteroids have been initiated, they must be tapered over ≥ 1 month to ≤ 10 mg/day oral prednisone or equivalent before atezolizumab can be resumed.

^b Atezolizumab may be withheld for a period of time beyond 105 days to allow for corticosteroids to be reduced to ≤ 10 mg/day oral prednisone or equivalent. The acceptable length of the extended period of time must be agreed upon by the investigator and the Medical Monitor.

^c Resumption of atezolizumab may be considered in patients who are deriving benefit and have fully recovered from the immune-mediated event. Patients can be rechallenged with atezolizumab only after approval has been documented by both the investigator (or an appropriate delegate) and the Medical Monitor.

Appendix 11

Risks Associated with Atezolizumab and Guidelines for Management of Adverse Events Associated with Atezolizumab

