Toxicities associated or possibly associated with atezolizumab treatment should be managed according to standard medical practice. Additional tests, such as autoimmune serology or biopsies, should be used to evaluate for a possible immunogenic etiology, *when clinically indicated*.

Although most immune-*mediated* adverse events observed with *atezolizumab* have been mild and self-limiting, such events should be recognized early and treated promptly to avoid potential major complications. Discontinuation of atezolizumab may not have an immediate therapeutic effect, and in severe cases, immune-*mediated* toxicities may require acute management with topical corticosteroids, systemic corticosteroids, or other immunosuppressive agents.

The investigator should consider the benefit–risk balance *for* a given patient prior to further administration of atezolizumab. In patients who have met the criteria for permanent discontinuation, resumption of atezolizumab may be considered if the patient is deriving benefit and has fully recovered from the immune-*mediated* event. Patients can be re-challenged with atezolizumab only after approval has been documented by both the investigator (or an appropriate delegate) and the Medical Monitor.

DOSE MODIFICATIONS

There will be no dose modifications for atezolizumab in this study.

TREATMENT INTERRUPTION

Atezolizumab treatment may be temporarily suspended in patients experiencing toxicity considered to be related to study treatment. If corticosteroids are initiated for treatment of the toxicity, they must be tapered over ≥ 1 month to ≤ 10 mg/day oral prednisone or equivalent before atezolizumab can be resumed. If atezolizumab is withheld for > 12 weeks after event onset, the patient will be discontinued from atezolizumab. However, atezolizumab may be withheld for > 12 weeks to allow for patients to taper off corticosteroids prior to resuming treatment. Atezolizumab can be resumed after being withheld for > 12 weeks if the Medical Monitor agrees that the patient is likely to derive clinical benefit. Atezolizumab treatment may be suspended for reasons other than toxicity (e.g., surgical procedures) with Medical Monitor approval. The investigator and the Medical Monitor will determine the acceptable length of treatment interruption.

Appendix 11

Risks Associated with Atezolizumab and Guidelines for Management of Adverse Events Associated with Atezolizumab (cont.)

MANAGEMENT GUIDELINES

PULMONARY EVENTS

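### The catch-all row of Appendix 10 Table 8 tells sites to resume atezolizumab after resolved severe toxicities for which Appendix 11 says to stop it permanently, and it does not defer to Appendix 11

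*Protocol*

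**What the plan says.** Appendix 10 governs adverse-event management in Arm A. The last row of its Table 8 (the hemorrhage table) is a residual rule for "Grade 3 or 4 or intolerable Grade 2 treatment-related toxicities not described above and Table 3 (dose modifications for cobimetinib"). All study treatment is withheld, and then "If event resolves to Grade 1 or better within 12 weeks, resume atezolizumab at fixed dose". Permanent discontinuation follows only if the event does not resolve in that time. Footnotes a, b and c are printed after the discontinuation sentence.

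Appendix 11 covers atezolizumab-associated events. For a number of severe immune-mediated events it orders permanent discontinuation and contact with the Medical Monitor. Its opening text allows a way back only as an exception: "In patients who have met the criteria for permanent discontinuation, resumption of atezolizumab may be considered if the patient is deriving benefit". Full recovery is also required, as is documented approval by the investigator and the Medical Monitor.

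Four other places bear on how the two fit together:

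- The note that opens Appendix 10: "For information regarding management of atezolizumab-associated adverse events, please refer to" Appendix 11.
- Section 5.1.5.3 sends Arm A immune-mediated reactions to Appendix 11, giving as examples, among others, "endocrine, ocular, myocarditis, pancreatic, dermatologic, neurologic, meningoencephalitis, and renal events".
- Section 4.6.2 lists among the mandatory reasons to stop: "Any adverse event that requires study treatment discontinuation per the guidelines in Section 5.1, Appendix 10, and Appendix 11".
- The general-guidance row of Appendix 10 begins "If atezolizumab is withheld and corticosteroids are initiated for an atezolizumab-related toxicity, corticosteroids must be tapered over" at least a month before resumption. Its footnote c adds "Patients can be rechallenged with atezolizumab only after approval has been documented by both the investigator" and the Medical Monitor.

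**The concern.** Two tables in the same protocol give opposite default instructions for the same event. A site managing an Arm A patient starts in Appendix 10, finds no row for the event, and arrives at the catch-all row, which says to resume once the event has resolved. Appendix 11 says the drug should already have been stopped for good.

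What is at stake is patient safety: re-exposure to atezolizumab after a severe immune-mediated toxicity, by default rather than by documented exception. No bearing on sample size, type I error, power or any planned analysis is claimed.

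**Working it through.** No arithmetic beyond a count applies; the check sets the two appendices side by side.

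**Step 1. Reach of the row.** It takes in any Grade 3-4 or intolerable Grade 2 treatment-related toxicity without an earlier row in Appendix 10. The earlier tables cover gastrointestinal, hepatic, dermatologic, pulmonary and ocular events, LVEF decrease, CPK elevation and rhabdomyolysis, and hemorrhage. Everything in the table below is therefore left to the catch-all row.

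**Step 2. Appendix 11 entries whose default is permanent discontinuation at a grade the row reaches.**

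| Appendix 11 table | Event | Corticosteroids directed by Appendix 11? |
|---|---|---|
| *First occurrence* | | |
| 4 | Life-threatening hyperthyroidism | No |
| 4 | Hypophysitis, Grade 4 | Yes |
| 6 | Myocarditis, Grade 3-4 | Yes |
| 8 | Pancreatitis, Grade 4 | Yes |
| 10 | Neuropathy, Grade 3-4 | No (institutional guidelines) |
| 10 | Myasthenia gravis or Guillain-Barré syndrome, any grade | No (to be considered) |
| 11 | Meningoencephalitis, all grades | Yes |
| 12 | Renal event, Grade 3-4 | Yes |
| 14 | Suspected HLH or MAS (ungraded) | No (to be considered) |
| *Recurrence* | | |
| 4 | Hypophysitis (recurrence handled as Grade 4) | Yes |
| 8 | Amylase/lipase elevation, Grade 3-4 | No (to be considered) |
| 8 | Pancreatitis, Grade 2-3 | Yes |

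First occurrence, by table: 2 + 1 + 1 + 2 + 1 + 1 + 1 = 9. Recurrence: 1 + 2 = 3. Total 9 + 3 = 12, in seven tables (4, 6, 8, 10, 11, 12 and 14). Of the nine, three start at Grade 3, three apply at any grade (so the row meets them from intolerable Grade 2), and three apply only at Grade 4 or when life-threatening.

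First Grade 3 pancreatitis, first Grade 3 hypophysitis and first amylase/lipase elevations are not counted: there Appendix 11 also withholds and then resumes. Recurrent Grade 3 myositis is not counted either, because the Grade 4 row to which it refers is not in the text available.

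**Step 3. Which guards apply.** The general-guidance row links its approval step to corticosteroids having been started. Appendix 11 directs corticosteroids in 5 + 2 = 7 of the 12 entries, and there the approval step arguably applies. In the other 4 + 1 = 5 it does not direct them, so that step need not be triggered.

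The remaining guard is footnote c in the catch-all row itself, and its scope is unclear. Where Appendix 10 separates the two branches, as for Grade 2 pneumonitis in its Table 4, footnote c sits on discontinuation and not on resumption. In the general-guidance row, and in the Table 2 row for raised transaminases with raised bilirubin, it sits on resumption.

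**Step 4. The clearest case.** A Grade 3 immune-mediated neuropathy resolves within 12 weeks.

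- Appendix 10, Table 8: resume atezolizumab at fixed dose.
- Appendix 11, Table 10: permanently discontinue and contact the Medical Monitor.
- Treatment is left to institutional guidelines, so the corticosteroid-linked approval may not arise.
- Section 5.2.3 does not list neuropathy other than Guillain-Barré syndrome as an adverse event of special interest, so a non-serious case need not be reported within 24 hours.

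Inside Appendix 10, only the ambiguous footnote c is left.

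**The case against.** The strongest reply is that the protocol, read as a whole, already settles the matter. Section 4.6.2 makes discontinuation mandatory for any event that requires it under Appendix 11. Section 5.1.5.3 and the opening note of Appendix 10 route these events there, and a residual row would normally yield to a table that names the event. The row's footnotes a and b concern tapering before resumption and longer withholding, so the cluster, footnote c included, can fairly be read as governing the whole instruction. Re-challenge after dual approval is possible under Appendix 11 too. Eight of the nine first-occurrence entries are adverse events of special interest, so the sponsor hears of them within 24 hours. For symptomatic LVEF decline, Appendix 10 Table 6 asks for discussion with the Medical Monitor before atezolizumab is resumed. The three recurrence entries are weaker, since the row is silent on recurrence.

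Much of this stands as mitigation. It means the defect is a contradictory default rather than an unguarded restart in every case, and that nine is the firmer count. It does not remove the conflict. Section 4.6.2 names Appendix 10 and Appendix 11 together and does not rank them. The opening note refers the reader to Appendix 11 without saying that it overrides. The examples in Section 5.1.5.3 do not include HLH/MAS. Rapid reporting adds oversight but leaves the opposite dosing instruction in print.

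**Conclusion.** The concern holds. Read as written, the catch-all row makes resumption of atezolizumab the default for nine Appendix 11 entries at first occurrence, and three on recurrence, where Appendix 11's default is permanent discontinuation. No text says which prevails. In seven of the twelve the approval step in the general-guidance row arguably applies, so the conflict there is one of default only; in the other five, Appendix 11 does not direct the corticosteroids that would trigger it.

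This rests on reading the phrase about toxicities not described above as referring to Appendix 10 alone, which is its plain sense. How many patients could be affected cannot be derived from the documents. The point should be corrected on safety grounds.

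**What to change.** Limit the row's atezolizumab instruction to toxicities described neither above nor in Appendix 11, and add that for events listed in Appendix 11 the site follows Appendix 11 for atezolizumab. Appendix 10 already does this in its rows for Stevens-Johnson syndrome or toxic epidermal necrolysis (Table 3) and for potential immune-mediated ocular toxicity (Table 5). Leave the cobimetinib instruction unchanged. No new clinical rule is introduced.

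The cost is one line in one table row, by clarification letter or with the next amendment. SAP Version 3, Section 2.5, says the study will be terminated early, so the change matters for Arm A patients still receiving atezolizumab.

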5.2.3 Adverse Events of Special Interest (Immediately Reportable to the Sponsor)

Adverse events of special interest are required to be reported by the investigator to the Sponsor immediately (i.e., no more than 24 hours after learning of the event; see Section 5.4.2 for reporting instructions). Adverse events of special interest for this study are as follows:

- Cases of potential drug-induced liver injury that include an elevated ALT or AST in combination with either an elevated bilirubin or clinical jaundice, as defined by Hy's Law (see Section 5.3.5.7) and based on the following observations:
 - Treatment-emergent ALT or AST $> 3 \times$ baseline value in combination with total bilirubin $> 2 \times$ ULN (of which $\geq 35\%$ is direct bilirubin)
 - Treatment-emergent ALT or AST $> 3 \times$ baseline value in combination with clinical jaundice
 - Hepatitis, including AST or ALT $> 10 \times$ ULN
 - Significant liver toxicity
- Suspected transmission of an infectious agent by the study treatment, as defined below
 - Any organism, virus, or infectious particle (e.g., prion protein transmitting transmissible spongiform encephalopathy), pathogenic or non-pathogenic, is considered an infectious agent. A transmission of an infectious agent may be suspected from clinical symptoms or laboratory findings that indicate an infection in a patient exposed to a medicinal product. This term applies only when a contamination of study treatment is suspected.
- Pneumonitis
- Colitis
- Endocrinopathies: diabetes mellitus, pancreatitis, adrenal insufficiency, hyperthyroidism, and hypophysitis
- Systemic lupus erythematosus

- Neurological disorders: Guillain-Barré syndrome, myasthenic syndrome or myasthenia gravis, and meningoencephalitis
- Events suggestive of hypersensitivity, IRRs, cytokine-release syndrome (CRS), influenza-like illness, HLH, and MAS
- Nephritis
- Ocular toxicities
 - Uveitis or retinitis
 - RVO
 - Serous retinopathy, including events of retinal detachment, retinal pigment epithelium detachment, neurosensory retinal detachment, and central serous chorioretinopathy
- Myositis
- Cardiac disorders for the following events
 - Grade ≥ 2 cardiac disorders, including atrial fibrillation, myocarditis, and pericarditis
 - Symptomatic heart failure or Grade ≥ 3 reduction in LVEF
- Vasculitis
- Myopathies, including rhabdomyolysis or Grade ≥ 3 CPK elevation
- Grade ≥ 3 hemorrhage or any-grade cerebral hemorrhage
- Grade ≥ 3 rash
- Grade ≥ 3 diarrhea

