
Grade 2^a Fever^b with hypotension not requiring vasopressors and/or Hypoxia requiring low-flow oxygen^d by nasal cannula or blow-by
	
 • Immediately interrupt infusion. • Upon symptom resolution, wait for 30 minutes and then restart infusion at half the rate being given at the time of event onset. • If symptoms recur, discontinue infusion of this dose. • Administer symptomatic treatment.^c • For hypotension, administer IV fluid bolus as needed. • Monitor cardiopulmonary and other organ function closely (in the ICU, if appropriate). Administer IV fluids as clinically indicated, and manage constitutional symptoms and organ toxicities as per institutional practice. • Rule out other inflammatory conditions that can mimic CRS (e.g., sepsis). If no improvement within 24 hours, initiate workup and assess for signs and symptoms of HLH or MAS as described in this appendix. • Consider IV corticosteroids (e.g., methylprednisolone 2 mg/kg/day or dexamethasone 10 mg every 6 hours). • Consider anti-cytokine therapy. • Consider hospitalization until complete resolution of symptoms. If no improvement within 24 hours, manage as per Grade 3, that is, hospitalize patient (monitoring in the ICU is recommended), permanently discontinue atezolizumab, and contact Medical Monitor.^e • If symptoms resolve to Grade 1 or better for 3 consecutive days, the next dose of atezolizumab may be administered. For subsequent infusions, consider administration of oral premedication with antihistamines, anti-pyretics, and/or analgesics and monitor closely for IRRs and/or CRS. • If symptoms do not resolve to Grade 1 or better for 3 consecutive days, contact Medical Monitor.

Appendix 11

Risks Associated with Atezolizumab and Guidelines for Management of Adverse Events Associated with Atezolizumab (cont.)

Table 7 Management Guidelines for Infusion-Related Reactions and Cytokine-Release Syndrome (cont.)

Event	Management

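### The ferritin cut-offs for HLH and MAS in Protocol Appendix 11 are each printed in two units that differ 1000-fold, so sites could classify the same result differently

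*Protocol*

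**What the plan says.** The HLH and MAS section of Protocol Appendix 11 sets out two classification rules.

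- **HLH:** "A patient should be classified as having HLH if five of the following eight criteria are met". One of the eight is "Ferritin > 500 mg/L (500 ng/mL").
- **MAS:** "A febrile patient should be classified as having MAS if the following criteria are met". Those criteria are "Ferritin > 684 mg/L (684 ng/mL") together with at least two of four further items (platelets, AST, triglycerides, fibrinogen).

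For each syndrome the text refers to published criteria and names the source. Table 7 of the same appendix covers infusion-related reactions and cytokine-release syndrome (CRS). Its Grade 2, 3 and 4 rows tell sites that, if there is no improvement within 24 hours, they should "initiate workup and assess for signs and symptoms of HLH or MAS as described in this appendix".

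Management is worded differently: "Patients with suspected HLH or MAS should be treated according to the guidelines in" Table 14, whose first step is to stop atezolizumab permanently and contact the Medical Monitor. Protocol Section 5.2.3 lists among the adverse events of special interest "Events suggestive of hypersensitivity, IRRs, cytokine-release syndrome (CRS), influenza-like illness, HLH, and MAS".

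**The concern.** In each ferritin line the bracketed figure should restate the first figure in another unit. It repeats the same number under a unit 1,000 times smaller, so each line states two different thresholds.

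The lists are written as decision rules. A patient is to be classified by them, and Table 7 sends unresolved CRS cases to them. For MAS, ferritin cannot be offset by other findings. In the other two-unit pairs the per-litre value comes first, so a site that works in per-litre units would naturally take the first, much higher, ferritin figure. Protocol Section 9.4 plans about 160 centres, and Section 5.3.5.2 asks for a diagnosis, where known, to be recorded instead of its component signs. The reading a site chooses could therefore change the adverse event term recorded for an Arm A patient, and that term feeds the summaries in SAP Section 4.5.2.

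**Working it through.** **Inputs.** All are from the HLH and MAS section of Appendix 11: the HLH ferritin line (500 in both units), the MAS ferritin line (684 in both units), and the remaining two-unit pairs as controls.

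**Conversion.** 1 mg/L = 1,000,000 ng / 1,000 mL = 1,000 ng/mL, and 1 µg/L = 1,000 ng / 1,000 mL = 1 ng/mL.

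**The printed equivalences cannot be reproduced.**

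| Line | First figure converted to ng/mL | Bracketed figure (ng/mL) | Ratio |
|---|---|---|---|
| HLH | 500 × 1,000 = 500,000 | 500 | 1,000 |
| MAS | 684 × 1,000 = 684,000 | 684 | 1,000 |

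With µg/L in place of mg/L, both lines agree exactly: 500 µg/L = 500 ng/mL and 684 µg/L = 684 ng/mL.

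**The other pairs in the two lists all reconcile.**

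- Haemoglobin: 90 g/L = 9 g/dL; 100 g/L = 10 g/dL.
- Platelets: 100 × 10⁹/L = 100,000/µL; 181 × 10⁹/L = 181,000/µL.
- ANC: 1.0 × 10⁹/L = 1,000/µL.
- Triglycerides: 265/2.992 = 88.57 and 156/1.761 = 88.59 mg/dL per mmol/L, the same factor to rounding.
- Fibrinogen: 1.5 g/L = 150 mg/dL, and for MAS "Fibrinogen ≤ 3.6 g/L (360 mg/dL") is also consistent.

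The fault is therefore confined to ferritin.

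**Range over which the two readings disagree.** For HLH, any ferritin above 500 and up to 500,000 ng/mL meets the ng/mL figure and fails the mg/L figure. For MAS the range is above 684 and up to 684,000 ng/mL.

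**Illustration.** Assume a result of 5,000 ng/mL, which is 5 mg/L. The documents give no such value; it is chosen only to show scale.

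- MAS: 5,000/684 = 7.3 times the ng/mL cut-off, but 5/684 = 0.73% of the mg/L figure.
- HLH: 5,000/500 = 10 times the ng/mL cut-off, but 5/500 = 1.0% of the mg/L figure.
- A patient with exactly four of the seven non-ferritin HLH criteria scores 5 of 8 (HLH) in ng/mL and 4 of 8 (not HLH) in mg/L.
- A febrile patient with two of the four further MAS items has MAS in ng/mL and does not in mg/L.

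The illustration does not depend on the value chosen. A result 100 times the ng/mL cut-off still reaches only 10% of the mg/L figure: 100 × 684 = 68,400 ng/mL = 68.4 mg/L, and 100 × 500 = 50,000 ng/mL = 50 mg/L. On the mg/L reading MAS would almost never be confirmed, while HLH could still be reached through five of the other seven criteria.

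**The case against.** The strongest objection is that the fault may lie in the text extraction. The difference is one character, µ read as m, and two identical misreadings of the same unit are not independent evidence. This cannot be excluded without the PDF. It is the less likely explanation, because the micro sign is rendered correctly in the per-microlitre counts in the same lists.

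A second objection is that no sensible site would be misled. The same number appears twice on one line, which looks like a slip in the unit, and the named published criteria give a puzzled investigator somewhere to turn. That lowers the chance of misuse. It does not settle which figure governs, because neither document says.

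The third objection concerns consequence, and most of it stands. Table 14 and the special-interest reporting rule both act before any classification. Ferritin is not in the screening or on-treatment laboratory panels of Protocol Section 4.5.6.1, so it would be measured only when a site chose to. No SAP analysis uses it. What remains is the confirmed diagnosis and the adverse event term recorded for it. CRS is itself an event of special interest, so even the count of such events need not change.

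**Conclusion.** The concern holds. As printed, both ferritin cut-offs contradict themselves by a factor of exactly 1,000, and nothing else in the protocol or SAP resolves them. The possible harm is inconsistent confirmation of HLH or MAS between sites in Arm A, most directly for MAS, where ferritin is mandatory. Stopping atezolizumab, expedited reporting, efficacy results, type I error, power and sample size are all unaffected. The point is minor.

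Two assumptions remain. The first is that the text reproduces the source PDF faithfully in these two lines. The second is that the ng/mL figures are the intended ones. The documents show that the units disagree; which unit is right has to come from the criteria they cite.

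**What to change.** Check the two lines against the source PDF and the two values against the published HLH and MAS criteria that Appendix 11 cites. If they are confirmed, replace mg/L with µg/L in both ferritin lines, so that they read 500 µg/L (500 ng/mL) and 684 µg/L (684 ng/mL), and send sites a short notice. The cost is a two-line correction and the notice, with no effect on data, sample size or analysis.
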